## **10.0 Local Number of Participants**

*10.1 Local Number of Participants to be Consented:* We plan to analyze data from at least 200 target participants. To account for attrition between sessions/replacement for incomplete data, up to 300 children may be consented/enrolled.

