Task-based analysis: Math under social evaluative stress In first level analyses (single subject, single-run), math performance will be modeled for each participant using a voxel-wise multiple regression analysis with a task predictor (math trials vs. blank trials), 24 regressors for head motion (Satterthwaite et al., 2013) and additional regressors to model censored data points (motion spikes). In subsequent analyses, we will explore the utility of including other time varying individual differences variables (e.g., heart rate, respiration) that are known to contribute to the BOLD signal. However, since these measures are expected to vary by stress condition, removing the effects of these physiological variables may unintentionally remove effects of interest. Particular care will be taken to reduce the confound of head motion by censoring (identifying as artifact) any data point with absolute motion greater than 2 mm (1 voxel) or a framewise displacement greater than 0.5 mm, as well as the immediately preceding and following data points. Data points with DVARS values exceeding the

individual's 75th percentile plus two times the interquartile range will also be censored. Participants with more than 25% of data points censored for artifact will be excluded from further analyses.

Second level analyses (single-subject, multiple runs) will test the within-subject contrast of math performed with judges (social evaluative stress) relative to math performed alone (without social evaluation) to identify brain regions differentially activated by social evaluative stress. Based on prior literature, we will examine activation in 5 *a priori* regions of interest, including "pain-related" brain regions (dorsal anterior cingulate [dACC], left and right anterior insula) and "safety-related" or regulatory brain regions (ventromedial prefrontal cortex [vmPFC], and left and right dorsolateral prefrontal cortex [dlPFC]). For each subject, the mean percent change in MR signal (averaged across voxels) between judged math and math alone will be extracted from each of these 6 regions. This analysis will generate the 6 task-related brain activation outcome variables (listed in section 4.3) for each participant.

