15.2 Power Analysis: For the power analysis for the primary analyses, we calculated the minimum detectable effect size (MDES) assuming  $n = 200$ ,  $\alpha = .05$ , and power = .80 with 12 covariates in our model. Power was estimated in R (R Core Team) using the pwr library (Champely, 2018). A power analysis was performed to quantify the minimum detectable effect size ( $f^2$ ) for a three-way interaction between social buffering condition, sex, and pubertal stage within a multiple regression model controlling for the 12 covariates, all two-way interactions, and the main effects (the most complex model considered in our primary analysis, see Equation 1 below). Assuming these conditions, we should be able to detect an  $f^2$  of 0.056. In

other words, adding the three-way interaction to a model containing the covariates and all lower order interactions and main effects, the three-way interaction would need to explain an additional 5.6% of the variability to be detected. This falls between Cohen's criteria for a small ( $f^2 = .02$ ) and medium effect ( $f^2 = .15$ ) (Cohen, 1988). With a sample size of 200, even if we lose 40 of the participants to movement artifact for the imaging analyses, assuming all the previous conditions but a sample size of 160, we will still have an  $f^2$  of .070, or still within a small-medium effect size. As the number of covariates decreases, the size of the MDSE will decrease. Therefore, this represents a conservative estimate of the power for our primary analyses as we are likely to have fewer covariates in our models and will use multiple imputation to correct for missing data. For the two-way interaction and main effects models, described below, the power will be larger than these reported values as the models will be simpler.

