Power Analysis for the Mediational Analysis: To assess power to detect mediation, we performed a Monte Carlo-based power analysis using simulated data. We varied the parameter values to roughly correspond to Cohen's criteria for small, medium, and large effects. This resulted in a total of 27 conditions, which we examined at our target sample size of 200. Each condition was replicated 2000 times and we calculated empirical power, which we defined as the proportion of times out of 2000 where we rejected the null hypothesis at  $\alpha = .05$ . Given the exploratory nature of this analysis and to simplify the simulation for the power analysis, we omitted covariates and did not vary the effects for the other condition contrasts (i.e., they were always fixed to 0). Next, we fit a path model using the lavaan package in R.

Our findings suggest that in order to detect mediation, the effect of condition on the mediator must be large and the effect of the mediator on the outcome must be medium or large. In addition, if the effect of condition on the outcome is not large, but small or medium sized, then we will be underpowered and would likely conclude complete mediation, when mediation may only be partial or non-existent. Based on this power analysis, it is likely that the MDES for the moderated mediation models will need to be at least medium to large as well.

Missing data. Because we will replace participants who do not come in for session 2 after doing session 1 (which is rare in our experience), we should have 200 completed participants. Missing data, however, could arise from problems in obtaining good imaging data. Participants also often fail to fully complete questionnaires and/or refuse to provide information on household income. If there is missingness in any of the dependent or independent variables, multiple imputation will be used (Little & Rubin, 2014; Peng, Harwell, Liou, & Ehman, 2006; Schafer & Graham, 2002). Variables related to the missingness and the variables missing data will be included in the missing data model. In the event that missingness is not at random (MNAR), we will investigate the use of models for non-ignorable missing data.

**15.4 Data Integrity:** Questionnaire data will be double-entered to reduce the likelihood of errors in data entry. Biospecimen data will be assayed in labs

that have standard quality control procedures. MRI data reviewed for raw data quality and artifact detection.

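### The plan does not say whether imaging outcomes from high-motion children are dropped or multiply imputed, and its imputation model is not stated to contain the interactions tested first

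*Combined protocol and SAP*

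**What the plan says.** Four places in the combined protocol and SAP bear on a child whose scan is spoiled by movement.

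- **Section 15.1, task-based analysis.** After the censoring rules for the math runs: "Participants with more than 25% of data points censored for artifact will be excluded from further analyses". The text does not say whether the 25% is judged per run or over the whole scan. The connectivity part of 15.1 models censored points but gives no exclusion threshold.
- **Section 15.2, power.** The detectable effect is recalculated at n = 160, "even if we lose 40 of the participants to movement artifact for the imaging analyses". The same paragraph calls the power estimate conservative, partly because the analysis "will use multiple imputation to correct for missing data".
- **Section 15.3, missing data.** "Missing data, however, could arise from problems in obtaining good imaging data", and "If there is missingness in any of the dependent or independent variables, multiple imputation will be used". The imputation model is described only as holding the variables with missing values and those related to missingness.
- **Section 10.1.** "We plan to analyze data from at least 200 target participants", and "To account for attrition between sessions/replacement for incomplete data, up to 300 children may be consented/enrolled".

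Section 15.1 counts 6 task-related and 6 connectivity-related primary imaging outcomes. Section 15.3 starts every primary analysis with the condition by sex by pubertal stage interaction.

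**The concern.** Neural activity stands first among the primary outcomes in section 3.1. For a high-motion child the documents leave open dropping the outcome, imputing it, or replacing the child. With no stated rule, the choice for 12 primary outcomes can be made after the results are known.

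Two further matters depend on that choice. If outcomes are imputed from a model without the interactions under test, the imputed values carry no interaction and pull the estimate toward zero. And if imputation is cited as support for power, a reader may believe it recovers the information lost with the 40 scans.

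The exclusion sentence also names participants and not runs. A child with a poor math run but good resting and speech-preparation runs has no defined status for the six connectivity outcomes.

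**Working it through.** **1. The plan's power figures.** Inputs from sections 5.1, 5.2 and 15.2: three conditions, puberty continuous, 12 covariates, alpha 0.05, power 0.80.

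Model degrees of freedom: 12 covariates + 4 main effects (2 + 1 + 1) + 5 two-way terms (2 + 2 + 1) + 2 three-way terms = 23. The test has u = 2 and v = n − 1 − 23 = n − 24. Power comes from the noncentral F distribution with λ = f²(u + v + 1).

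| n | v | Detectable f², recomputed | Stated in 15.2 | Power at the stated f² |
|---|---|---|---|---|
| 200 | 176 | 0.0548 | 0.056 | 0.81 |
| 160 | 136 | 0.0709 | 0.070 | 0.79 |

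Both figures reproduce closely. The n = 160 row describes models from which 40 of 200 children (20%) are absent, not models with imputed outcomes.

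**2. Imputing without the interaction.** Suppose a fraction m of outcomes is missing at random and imputed from a model with main effects only. Observed children carry the true interaction and imputed children carry none, so the expected estimate is about (1 − m) × true value + m × 0. With m = 40/200 = 0.20 and a true value of 0.50, this is 0.80 × 0.50 = 0.40, a 20% shrinkage.

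**3. Simulation check.** The assumed design is two equal groups, n = 200, standard normal puberty score, residual SD 1, group by puberty interaction 0.50, 40 outcomes missing at random, 20 imputations, 600 replicates and no auxiliary variables.

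| Analysis | Mean estimate | Empirical SE |
|---|---|---|
| Full data, n = 200 | 0.50 | 0.143 |
| Complete cases, n = 160 | 0.51 | 0.161 |
| Imputation with the interaction | 0.51 | 0.162 |
| Imputation without the interaction | 0.40 | not compared (biased) |

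The means of 0.51 differ from 0.50 only by simulation noise. The complete-case SE exceeds the full-data SE by 0.161/0.143 = 1.13, close to √(200/160) = 1.12. Correct imputation does not reduce it. A separate simulation of a condition by puberty interaction agreed: 0.40 without the terms and 0.51 with them, with an SE of 0.211 for both complete cases and correct imputation, against 0.186 with full data.

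**4. Scope of the exclusion.** The sentence closes the first-level paragraph of the task fMRI analysis, and the second-level analyses follow directly. Section 15.2 describes the loss as "lose 40 of the participants to movement artifact for the imaging analyses". Section 15.3 fits a separate model for each dependent variable. No section drops cortisol or heart-rate data because of head motion.

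**The case against.** The two rules can be read in sequence: a failed scan leaves image processing, the extracted value becomes missing, and the regression stage imputes it. Section 15.1 does separate those stages, and n = 160 is a what-if calculation, not a defined analysis set. This reading is possible, but the text does not state it, and a power calculation at n = 160 speaks against it. The need for one explicit rule stands.

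Section 15.3 is silent on interaction terms and does not say they will be omitted. That is correct, so the 20% shrinkage is conditional. Imputation can also recover information when covariates such as income are missing, or when strong auxiliaries exist. That stands too, but section 15.2 ties no auxiliary to the imaging outcomes, so imputation does not support the imaging power as written. Replacement under section 10.1 could reduce the loss of 40, but whether it covers motion failures is not stated.

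A reader might infer stronger claims:

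- **Cortisol and heart-rate data will be discarded.** Taken literally with 40 children lost, those models would fall to n = 160, and power at f² = 0.056 would drop from 0.81 to 0.69. The context in step 4 points the other way, so this is loose wording.
- **The exclusion selects calmer children.** Nothing in the documents shows this.
- **The power figures are wrong.** They reproduce.

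**Conclusion.** The point holds for the imaging outcomes. The plan gives unreconciled treatments for 12 primary outcomes and leaves the reach of the 25% rule undefined. If outcomes are imputed without the tested interactions, an interaction shrinks by about the fraction missing: 20% at the plan's own what-if loss of 40. This assumes outcomes missing at random and no auxiliary that carries the interaction. Without informative auxiliaries, correct imputation gives complete-case precision, so the honest imaging figure is the plan's own f² of about 0.07 at n = 160. Complete-case and imputed analyses are both defensible as primary. The defect is that neither is named.

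**What to change.** 1. In section 15.1, set to missing only the outcome or outcomes from the affected run, keep the child in all other analyses, and say that the 25% is judged per run. Apply the same rule to the resting and speech-preparation runs.
2. In section 15.3, name either complete-case or imputed imaging outcomes as primary and the other as sensitivity.
3. Where outcomes are imputed, include the condition by sex by puberty terms and all lower-order terms, with cortisol, heart rate and motion as auxiliaries.
4. In section 15.2, keep n = 160 (f² about 0.07) as the imaging power and delete imputation as a reason it is conservative.

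The cost is a slightly larger imputation model and a slightly less favourable power statement. No new data are needed.

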### 2.3 Study Aims:

The current study examines the neural response, as well as the cortisol hormonal response to social evaluative stress across the transition to puberty. We use a modified version of the Trier Social Stress Test (TSST) in the MRI scanner (called the Minnesota Imaging Stress Test in Children; MISTiC) to elicit social evaluative stress. In this project, we will randomly assign youth to complete this testing under one of three social buffering conditions: presence of a parent, presence of an experimenter (stranger), or no social support present (standard imaging condition).

The **long-term goal** of our research is to enrich understanding of stress regulation and its role in human development. The **overall objective** of this project is to understand normative processes in stress regulation and their neurobiological correlates as children leave childhood and become more autonomous in adolescence. The **central hypothesis** of this project is that early adolescence is a period of time when parental buffering wanes in efficacy, leaving many youth experiencing a relative dearth of relationships that can provide powerful stress buffers.

**The aim of the current study is to delineate changes in brain activation in response to social buffering by parents over the pubertal transition.**

**Hypothesis #1:** Parental social buffering will result in increased activation in brain regions associated with safety (e.g. vmPFC) and lower activation in brain regions involved in fear and pain (e.g., insula, amygdala, hypothalamus), as well as tighter coupling between the vmPFC and amygdala activity, but these relationships will wane with pubertal development.

**Hypothesis #2:** Neural activity associated with social buffering will mediate the effectiveness of physiological buffering by social partners.

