## 9.2 Additional Safeguards:

Children are the targeted population for this study. Others that have been checked as “allowed” above are not being intentionally included or excluded. For example, we will not inquire about someone’s membership in a disenfranchised group, nor whether a target child’s parent is on active duty in the military. Our careful consent/assent procedures, designed to handle research with children, should be sufficient to cover other vulnerable participants who may inadvertently enter our study.

All of the subjects will be children, ranging 11-14 years old. This study focuses on adolescents because our goal is an analysis of the impact of social buffering and puberty on stress-mediating systems. Children have been the focus of our research for the past 30+ years. Our staff members are highly trained in working with children and families. The graduate students working on the project will be Child Psychology and/or Child Clinical Psychology Ph.D. students. The undergraduate research assistants will, for the most part, be majoring in child development.

Much of the work will be performed online over video conferencing. Staff will guide parents and children through the study procedures and participating families will likely be comfortable in their own homes.

Our laboratory has been scanning both typically developing children and adolescents (ages 4-17) and those at risk due to early health or environmental risks for over two decades. We have conducted NIH funded research with child participants at the CMRR for the past 16 years. We are very experienced in putting children at ease in the MRI scanner and ensuring that children are aware that they can stop at any time. We have completed a prior MRI study with 11- to 14-year-olds using the MISTiC social stress paradigm; therefore, we are confident that we are well positioned to properly inform children about the procedures and are not stressing children beyond normal everyday levels that they experience in school or in extracurricular activities (sports competitions; music, dance, or drama performances; etc.).

Parents provide consent, youth provide assent, and see below where that process is fully described to ensure that youth have full understanding and are free to decline participation.

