Given that the MISTiC paradigm has not been used previously, it is possible that the most prominent regions of activity for this task may not match the *a priori* regions identified from the prior stress and social buffering literature. Therefore, we will also conduct an exploratory group-level analysis to identify primary regions of activation for the same socially evaluative math vs. non-evaluative math conditions (judged math vs. math alone, cluster corrected  $p < .005$ ). Because we expect that social buffering will alter the activity difference between social evaluative and non-evaluative math periods, we will use only the control condition (no social partner) to identify regions activated by this task. In the resultant group-level map, we will identify up to 4 primary regions of activation by selecting clusters that meet the cluster-corrected  $p < .005$  threshold, and then rank-ordering those regions by maximal z-statistic. Mean percent change in signal will be extracted for each participant (across all four buffering conditions) using anatomical masks derived from this analysis conducted in the control (no social partner) group. Therefore, exploratory analyses may generate up to 4 additional task-related MRI outcome variables.

Connectivity analysis: Speech preparation We are also interested in the neural correlates of anticipatory stress during the speech preparation period. However, the speech preparation period does not contain distinctive event markers needed for task-based fMRI analyses. Thus, to address the neural correlates of stress during speech preparation, we will use a seed-based connectivity approach to examine strength of functional connectivity between *a priori* seed regions of interest in the limbic system (amygdala, insula, hypothalamus) and target regions in the prefrontal

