### 15.3 Statistical Analysis of MRI and non-MRI Outcome Variables:

The following is a list of the analyses that we will perform on the outcome measures. They are classified as to whether they are the primary or mediational analyses. All statistical analyses will be performed in R.

The primary analyses will consist of a series of multiple regression models. For each dependent variable, variation in neural activity, cortisol response, and heart rate response, we will begin by testing the three-way interaction between social buffering condition, sex, and pubertal stage for all outcomes. If the three-way interaction is not significant, we will then examine all two-way interactions. If the two-way interactions are not significant, we will then examine main effects only models. If the three-way interaction is significant, we will not examine any other model. If condition is significant as an interaction or as a main effect, we will examine all pairwise comparisons using Tukey's Honestly Significant Difference test.

Multiplicity of testing. We will correct for multiple comparisons using the Benjamini-Hochberg (BH) correction. The BH method works by controlling the false discovery rate, and relative to the Bonferroni's correction is more powerful, while still adequately protecting against Type I error (Williams, Jones, & Tukey, 1999).

Mediational Analysis. When changes in activity of brain regions differ by condition or condition by pubertal status and we also see condition or condition by pubertal status differences for cortisol, or heart rate, then we will examine whether brain activity differences mediate the neuroendocrine or autonomic differences. This will be examined using path analysis, while controlling for covariates identified in the preliminary

covariate analysis, and will be estimated using the lavaan package in R (Rosseel, 2012).

The significance of all indirect effects will be assessed using bias-corrected 95% confidence intervals (Efron & Tibshirani, 1986), where confidence intervals that are non-overlapping with zero will be considered significant.

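### Exploratory brain regions are chosen on the control arm's own response and then used to compare that arm with the parent and stranger arms, which biases those comparisons

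*Combined protocol and SAP*

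**What the plan says.** Section 15.1 plans an exploratory search in case the stress task activates regions other than the a priori ones. It contrasts judged math with math alone at a cluster-corrected p < .005, ranks the surviving clusters by peak z and keeps at most 4. The search sample is one arm: "we will use only the control condition (no social partner) to identify regions activated by this task". The reason given is that buffering is expected to change the contrast.

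The plan continues: "Mean percent change in signal will be extracted for each participant (across all four buffering conditions) using anatomical masks derived from this analysis". It adds that "exploratory analyses may generate up to 4 additional task-related MRI outcome variables". Section 15.1 sends the imaging outcome variables to the general analyses. Section 15.3 states that "we will begin by testing the three-way interaction between social buffering condition, sex, and pubertal stage for all outcomes", moves to two-way interactions and then main effects when the higher-order terms are not significant, and follows a significant condition term with all Tukey pairwise comparisons. Benjamini-Hochberg (BH) correction is applied for multiplicity.

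Mediation is examined when brain activity differs by condition or condition by puberty "and we also see condition or condition by pubertal status differences for cortisol, or heart rate". Exploratory regions are not excluded from that trigger.

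**The concern.** The contrast that selects a region is the contrast later tested, and the control children supply both. A region is kept because its control mean was high, and part of that height is chance. The other two arms played no part in the selection, so their means carry no matching lift. The difference between control and either buffered arm is therefore shifted upward even when condition has no effect.

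Sections 15.1 and 15.3 describe no split sample, leave-one-out step, independent localizer or external mask. The stated reason for using controls concerns sensitivity and does not address this dependence. BH and Tukey allow for the number of tests; they do not re-centre a shifted mean.

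Hypothesis 1 in section 2.3 predicts, with a parent present, "lower activation in brain regions involved in fear and pain". In such regions the artefact imitates the predicted result. In safety regions, where higher activation with a parent is predicted, it works against the hypothesis. A false condition difference could also help open the mediation analysis, but only if cortisol or heart rate differs as well.

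**Working it through.** **Inputs from the documents.** Three arms (section 5.1); 200 children analysed (section 10.1); 160 if 40 are lost to motion (section 15.2). Equal allocation is an assumption, as no ratio is stated: 200/3 ≈ 67 and 160/3 ≈ 53 per arm.

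**The plan's own figure.** No figure is given for the exploratory analysis. The nearest is the detectable f² of 0.056 for the three-way interaction (0.070 at n = 160). With three arms there are 12 covariates + 4 main-effect + 5 two-way + 2 three-way terms = 23 predictors, so u = 2 and v = 200 − 23 − 1 = 176. This gives f² = 0.0548, and 0.0709 at n = 160. Four arms would give 0.0634 and 0.0826. The power statement therefore fits three arms, and the reference to four conditions in the extraction sentence does not.

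**Why the dependence exists.** Let each arm mean have variance σ²/n. Then Cov(control mean, control − parent) = σ²/n, and their correlation is (σ²/n) / [(σ/√n) × σ√(2/n)] = 1/√2 ≈ 0.71. Selecting on the first moves the second. For the mean pooled over all N children, the covariance with the difference between any two arms i and j is (n_i/N)(σ²/n_i) − (n_j/N)(σ²/n_j) = 0, whatever the arm sizes, if variances are equal.

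**One fixed region, kept if control z > 2.576.** With true effect d and m = d√n, the inflation of the control mean is φ(2.576 − m) / [1 − Φ(2.576 − m)] / √n. For n = 67 and d = 0.2, m = 1.637 and 2.576 − m = 0.939; the ratio is about 1.48, and 1.48/8.185 = 0.18 SD. The two-sided 5% control-versus-parent test then rejects 12.0%. At d = 0.3 the inflation is 0.11 SD and rejection 5.5%; at d = 0.4, 0.05 SD and 3.6%; at d = 0.8, about nil and 5.0%.

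**Several regions, ranked.** Assumptions: K = 50 or 100 independent regions; true means from N(0, τ²), identical in all arms; between-child SD 1; a region qualifies at one-sided p < .005/K (a stand-in for cluster correction); at most the top 4 are kept; the tested mean is that of the selected region. Where two values are given they are for K = 50 and K = 100. Bias and rejection are per selected region, with no multiplicity adjustment.

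| n per arm | τ | Trials with any region passing | Bias (SD) | Condition test rejects |
|---|---|---|---|---|
| 67 | 0.1 | .08; .10 | .290; .301 | .375; .426 |
| 67 | 0.2 | .68; .83 | .153; .155 | .127; .126 |
| 67 | 0.3 | .97; 1.00 | .089; .099 | .069; .078 |
| 53 | 0.1 | .06; .06 | .367; .392 | .524; .584 |
| 53 | 0.2 | .50; .65 | .191; .203 | .157; .182 |
| 53 | 0.3 | .92; .98 | .118; .125 | .086; .085 |

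The τ = 0.1 rates rest on 308 to 592 selected regions per setting and are approximate. At 67 per arm and τ = 0.2 to 0.3, control versus parent rejects 8 to 13%. Parent versus stranger and condition by puberty stay near nominal, at about 4 to 5%. With pooled selection, the bias in the arm difference is within 0.003 SD and the condition test rejects 4.7 to 5.9%.

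**Effect of the mask.** In smooth simulated 3D maps at 67 per arm, using the cluster itself as the mask gives inflation of 0.47 SD at a true peak d of 0.3 and 0.19 SD at 0.7, with control-versus-parent type I error of 0.85 and 0.20. Whole anatomical parcels give 0.23 and 0.06 SD, with 0.29 and 0.05.

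**The case against.** The direction of the bias is hard to dispute; the case on the other side concerns its weight.

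- **The rates above ignore the plan's own error control.** This is fair. Section 15.3 requires BH, but does not define the family. If BH is applied across the selected regions plus 14 null outcomes (12 imaging, cortisol, heart rate), per-region rejection at τ = 0.2 to 0.3 falls to roughly 0.5 to 3%. The null baseline falls too: at 67 per arm and τ = 0.2 it is about 1.5% with control-only selection against 0.2% with pooled selection, although at τ = 0.3 there is no clear difference. BH protects less if other outcomes have real effects, and it leaves the biased estimates in place.
- **The highest rates are conditional on a rare event.** At τ = 0.1 a region passes in only 6 to 10% of trials. Multiplying through for 67 per arm and K = 50, .08 × .375 ≈ 3% of trials.
- **The plan says anatomical masks.** Averaging over a wider area dilutes the bias, and with strong activation it can vanish. The ranked-region model does not represent that dilution. The size is therefore uncertain; the direction is not.
- **The analysis is exploratory and the control-only choice is deliberate.** Both are true, and they limit the severity. However, the plan runs this search because the a priori regions may miss the main activity, so these outcomes could become prominent. Reading section 15.3's reference to all outcomes as covering them is natural, though the plan does not say so explicitly.

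**Conclusion.** The concern holds. As written, control-versus-parent and control-versus-stranger differences in the exploratory regions, and the condition main effect there, are biased towards higher control activation. With no condition effect, equal arms and moderate regional effects, the bias is about 0.09 to 0.16 SD at 67 per arm and 0.12 to 0.20 SD at 53. Unadjusted condition-test rejection is 7 to 13% and about 9 to 18%. BH brings false declarations well below these rates but does not correct the estimates. True activation and mask size are not in the documents, so these figures show a range and are not a forecast.

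The 12 a priori imaging outcomes are untouched. Parent versus stranger is not biased, and condition by puberty stayed near nominal in the moderate settings. This should be fixed, but it does not threaten the primary analysis.

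**What to change.** In section 15.1, define the exploratory regions from all children in the three arms pooled, each counted once, without regard to condition. This needs one or two sentences and no new data.

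The cost is sensitivity when buffering is strong. If both buffered arms suppress a fraction s of the control response, pooled z divided by control-only z is √3 × (3 − 2s)/3: 1.73 at s = 0, 1.15 at s = 0.5, 1.00 at s = 0.63 and 0.58 at s = 1. Pooling is less sensitive only when average suppression exceeds (3 − √3)/2 ≈ 63%. If just one arm suppresses the region fully, the ratio is √3 × 2/3 = 1.15.

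Alternatives:

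- **Independent data.** Section 9.2 reports: "We have completed a prior MRI study with 11- to 14-year-olds using the MISTiC social stress paradigm". If that study provides this contrast, it could supply the regions. Section 15.1 says the opposite, "Given that the MISTiC paradigm has not been used previously", and the two statements must be reconciled first.
- **Split the control arm.** Selecting in one half and testing in the other restores the nominal rate (0.050 simulated). For an illustrative d = 0.5, power falls from 0.82 (67 v 67) to 0.65 (33 v 67).
- **Keep control-only selection.** Report control-versus-buffered differences in these regions descriptively, test only parent versus stranger there, and do not let a control contrast in these regions trigger mediation.

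Separately, correct the reference to four buffering conditions to match the three-arm design.
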